# *Old Civil Hospital of Guadalajara* "FRAY ANTONIO MAYOR"

---

all      23      Dextran Iron      1

Version 2.0, 29 June 2023

Effect of intravenous iron repletion on renal function in patients with iron deficiency and acute kidney injury, clinical trial. June 2023, HCG/CEI-1232/22

[name] [contact], [name] GUADALAJARA, JAL

# Old Civil Hospital of Guadalajara

## "FRAY ANTONIO MAYOR"

Teaching Subdirectorato  
Research Coordination

all	24	placebo	2
all	25	placebo	2
all	26	placebo	2
all	27	Dextran Iron	1
all	28	placebo	2
all	29	placebo	2
all	30	Dextran Iron	1
all	31	placebo	2
all	32	Dextran Iron	1
all	33	placebo	2
all	34	placebo	2
all	35	placebo	2
all	36	Dextran Iron	1
all	37	Dextran Iron	1
all	38	Dextran Iron	1
all	39	Dextran Iron	1
all	40	Dextran Iron	1
all	41	placebo	2
all	42	placebo	2
all	43	Dextran Iron	1
all	44	placebo	2
all	45	placebo	2
all	46	Dextran Iron	1
all	47	Dextran Iron	1
all	48	placebo	2
all	49	Dextran Iron	1
all	50	placebo	2
all	51	placebo	2
all	52	Dextran Iron	1
all	53	placebo	2
all	54	placebo	2
all	55	Dextran Iron	1
all	56	placebo	2
all	57	Dextran Iron	1
all	58	Dextran Iron	1

Version 2.0, 29 June 2023

[name] [contact], [name] GUADALAJARA, JAL

Effect of intravenous iron repletion on renal function in patients with iron deficiency and acute kidney injury, clinical trial. June 2023, HCG/CEI-1232/22

## Old Civil Hospital of Guadalajara "FRAY ANTONIO MAYOR"

Teaching Subdirectorato  
Research Coordination

all	59	Dextran Iron	1
all	60	Dextran Iron	1
all	61	placebo	2
all	62	placebo	2
all	63	Dextran Iron	1
all	64	placebo	2
all	65	Dextran Iron	1
all	66	Dextran Iron	1
all	67	placebo	2
all	68	placebo	2
all	69	placebo	2
all	70	placebo	2
all	71	placebo	2
all	72	Dextran Iron	1
all	73	Dextran Iron	1
all	74	Dextran Iron	1
all	75	Dextran Iron	1
all	76	placebo	2
all	77	placebo	2
all	78	placebo	2
all	79	Dextran Iron	1
all	80	Dextran Iron	1
all	81	placebo	2
all	82	Dextran Iron	1
all	83	Dextran Iron	1
all	84	placebo	2
all	85	Dextran Iron	1
all	86	placebo	2
all	87	Dextran Iron	1
all	88	placebo	2
all	89	Dextran Iron	1
all	90	Dextran Iron	1
all	91	placebo	2
all	92	Dextran Iron	1
all	93	placebo	2

Version 2.0, 29 June 2023

[name] [contact], [name] GUADALAJARA, JAL

Effect of intravenous iron repletion on renal function in patients with iron deficiency and acute kidney injury, clinical trial. June 2023, HCG/CEI-1232/22

## Old Civil Hospital of Guadalajara "FRAY ANTONIO MAYOR"

Teaching Subdirectorato  
Research Coordination

all	94	placebo	2
all	95	placebo	2
all	96	placebo	2
all	97	placebo	2
all	98	Dextran Iron	1
all	99	Dextran Iron	1
all	100	placebo	2
all	101	Dextran Iron	1
all	102	placebo	2
all	103	Dextran Iron	1
all	104	Dextran Iron	1
all	105	placebo	2
all	106	placebo	2
all	107	placebo	2
all	108	Dextran Iron	1
all	109	placebo	2
all	110	Dextran Iron	1
all	111	Dextran Iron	1
all	112	placebo	2
all	113	Dextran Iron	1
all	114	Dextran Iron	1
all	115	placebo	2
all	116	placebo	2
all	117	Dextran Iron	1
all	118	Dextran Iron	1
all	119	placebo	2
all	120	placebo	2

Version 2.0, 29 June 2023

, and members of the nephrology staff, blinded to the allocation groups, administered the drugs to each patient every day.

All patients will have a detailed medical history and physical examination. Complete blood count, serum creatinine, serum urea, serum urea nitrogen, serum electrolytes, and blood test parameters were measured daily.

# Old Civil Hospital of Guadalajara

## "FRAY ANTONIO MAYOR"

Teaching Subdirectorato  
Research Coordination

urine. The test will be presented in accordance with the CONSORT 2010 explanation and elaboration guide. Continuous variables will be presented as mean (SD) when they are normally distributed or as medians (interquartile range [IQR]) in the case of abnormal distribution, following the test Shapiro-Wilk. One way ANOVA was used to compare differences between groups. Categorical variables expressed as proportions will be compared with Fisher's  $\chi^2$  test or the exact test, as appropriate. For the rest of the tests, p values were two-tailed;  $p < 0.05$  will be considered statistically significant. Statistical analysis and graphics will be performed with the statistical software MedCalc (Ostend, Belgium, see 19.1.3).

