## 2.4 SCIENTIFIC BACKGROUND

Acute kidney injury (AKI) is a serious complication that is independently associated with poor outcomes [1, 2]. Approximately one in five patients with non-severe sepsis develops AKI [3], which increases to two-thirds in critically ill patients. About 50% of ICU patients with AKI die (4-12), and those who survive an episode of AKI have a higher risk of progressing to chronic kidney disease (CKD). Currently, there are few pharmacological therapeutic options available to prevent or treat AKI, and management is limited to alleviating hemodynamic and toxic renal lesions. support measures, such as dialysis.

Iron deficiency occurs in up to 30% of hospitalized patients and has been linked to worse clinical evolution, even in the absence of anemia. This iron deficiency is worse even when anemia figures are reached. It has been documented that critically ill patients develop anemia as part of the process of their pathology. It has been seen that during processes of exacerbation of pathologies such as heart failure, the administration of intravenous iron avoids the probability of hospitalization and clinical evolution (13-16). It has been shown that in DRA there is mitochondrial dysfunction (17), specifically in the renal tubule where the greatest amount of mitochondria is concentrated,

Version 2.0, 29 June 2023

Effect of intravenous iron repletion on renal function in patients with iron deficiency and acute kidney injury, clinical trial. June 2023, HCG/CEI-1232/22

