### 2.5 OBJECTIVES

#### **Primary objective:**

The endpoint of interest was the proportion of patients meeting one or more criteria for Major Adverse Kidney Events within 30 days (MAKE30): in-hospital mortality; receipt of new RRT; or persistent renal dysfunction.

In hospital mortality was defined as death from any cause prior to hospital discharge censored at 30 days after ICU admission. Receipt of new RRT was defined as receipt of any modality of RRT between ICU admission and the first of (1) hospital discharge or (2) 30 days in a patient not known to have received RRT prior to ICU admission. Persistent renal dysfunction was defined as a final serum creatinine value before hospital discharge (censored at 30 days after enrollment) that was  $\geq 200\%$  of the baseline creatinine value.

And will be evaluated at 60 and 90 days.

**Secondary objectives:** all the following will be at hospital discharge and 28 days after hospital discharge between the intervention group (iron replacement) compared to the control group (placebo).

- ferritin value, (pg/dL)
- transferrin saturation (%)
- Hemoglobin (g/dL)
- serum creatinine (mg/dL)
- start of renal support therapy (any type of renal support such as: intermittent hemodialysis, peritoneal dialysis or continuous therapies)
- recovery of renal function, considered as a decrease in serum creatinine and approaching  $<0.3\text{mg/dL}$  of basal creatinine
- death

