## 2. DESIGN OF THE STUDY

Randomized placebo-controlled clinical trial, randomization method in blocks of 5 by frequency of occurrence. In patients with acute kidney injury, they will be randomized to receive the administration of intravenous iron dextran in a single exhibition according to the Mg provided by the Virizzi formula compared to placebo.

The sample size determined 55 patients per group, with a standard deviation of 1.5.

$$n = [(Z_{\alpha/2} + Z_{\beta})^2 \times \{2(\sigma)^2\}] / (\mu_1 - \mu_2)^2$$
$$n = [(1.96 + 0.84)^2 \times \{2(1.5)^2\}] / (10.8 - 10)^2$$
$$n = 55,125$$

n = sample size required in each group  $\mu_1 - \mu_2 =$   
clinically significant difference = 0.8 or = standard  
deviation = 1.5

$Z_{\alpha/2}$ : 1.96

$Z_{\beta}$ : 0.84

Version 2.0, 29 June 2023

Effect of intravenous iron repletion on renal function in patients with iron deficiency and acute kidney injury, clinical trial. June 2023, HCG/CEI-1232/22

[name] [contact], [name] GUADALAJARA, JAL

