### 4.1 INCLUSION AND EXCLUSION CRITERIA

#### criteria of **inclusion**:

Hospitalized patients with ARD, will be defined as the diagnosis using the KDIGO criteria of serum creatinine (Cr); Patients with AKI  $> 18$  and  $< 85$  years, baseline creatinine  $< 2$  mg/dL and with written informed consent will be included.

Iron deficiency according to the criteria of the 2: serum iron  $< 13$  ng/dL, transferrin saturation  $< 20\%$ .

Version 2.0, 29 June 2023

Effect of intravenous iron repletion on renal function in patients with iron deficiency and acute kidney injury, clinical trial. June 2023, HCG/CEI-1232/22

[name] [contact], [name] GUADALAJARA, JAL

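### Continuous secondary outcomes are compared by unadjusted one-way ANOVA although pre-randomisation values of most of them are available; baseline-adjusted ANCOVA would be more precise at no data cost

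*Protocol*

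**What the plan says.** The statistical paragraph of Section 2 (Design of the Study, after the allocation list) says of continuous variables: "One way ANOVA was used to compare differences between groups". Categorical variables get a chi-square or Fisher exact test. No covariate, regression, change-from-baseline model or rank test appears anywhere in the Protocol. The same paragraph expects that some continuous variables will not be normal and will be summarised "or as medians (interquartile range [IQR]) in the case of abnormal distribution", but names no different test for them.

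The ANOVA sentence names no outcome. The continuous outcomes it can apply to are the secondary ones in Section 2.5: ferritin, transferrin saturation, haemoglobin and serum creatinine, for which "all the following will be at hospital discharge and 28 days after hospital discharge".

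On values available before treatment:
- Section 4.1 bases the AKI diagnosis on creatinine ("will be defined as the diagnosis using the KDIGO criteria of serum creatinine (Cr") and lists a transferrin saturation below 20% among the iron-deficiency criteria.
- Section 2 states: "Complete blood count, serum creatinine, serum urea, serum urea nitrogen, serum electrolytes, and blood test parameters were measured daily".

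On sample size, Section 2 says: "The sample size determined 55 patients per group, with a standard deviation of 1.5". The difference used is 0.8 (10.8 against 10). The variable is not named; the values suggest haemoglobin.

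**The concern.** With two groups, one-way ANOVA is the two-sample t-test (F = t²), so it makes no use of what is known about each patient before randomisation. Haemoglobin, creatinine and transferrin saturation at discharge probably depend in part on their values at entry. Leaving that variation in the error term widens the confidence intervals and leaves chance baseline imbalance uncorrected.

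This is a loss of precision, not of validity. It matters because there is little precision to spare: the sample size gives just under 80% power for the variable it was built on and makes no allowance for missing readings. Section 2.4 gives a background figure ("About 50% of ICU patients with AKI die") that suggests an appreciable share of patients may have no discharge or later value. The primary MAKE30 comparison is a proportion and is not touched.

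**Working it through.** **Inputs from the Protocol (Section 2).** Difference 0.8, SD 1.5, 55 per arm, two-sided 5%, Z values 1.96 and 0.84. The Protocol gives no baseline-outcome correlation r, so 0.1 to 0.7 is an assumed range.

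**1. The stated sample size reproduces.** n = (1.96 + 0.84)² × 2 × 1.5² / 0.8² = 7.84 × 4.5 / 0.64 = 55.125 per arm.

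**2. Unadjusted ANOVA of the final value, 55 per arm.**
- Standard error = 1.5 × √(2/55) = 0.286.
- Noncentrality = 0.8 / 0.286 = 2.80, with 108 df and critical t 1.982.
- Power 0.7916; 95% CI half-width 1.982 × 0.286 = 0.567.

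**3. ANCOVA on the baseline value, 55 per arm.** Residual SD = 1.5 × √(1 − r²), with 107 df.

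| r (assumed) | Residual SD | Power | CI half-width | CI width relative to ANOVA |
|---|---|---|---|---|
| 0 | 1.500 | 0.7915 | 0.567 | 1.000 |
| 0.1 | 1.492 | 0.80 | 0.564 | 0.995 |
| 0.3 | 1.431 | 0.83 | 0.541 | 0.954 |
| 0.5 | 1.299 | 0.89 | 0.491 | 0.866 |
| 0.7 | 1.071 | 0.97 | 0.405 | 0.714 |

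The power column holds only for the variable behind the sample size. The last column, √(1 − r²), applies to any of the outcomes on its own analysis scale.

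**4. Validity.** In simulation with 55 per arm and no true effect (4,000 runs per setting), both methods rejected about 5% of the time: ANOVA 0.050 and 0.051, ANCOVA 0.048 and 0.054, at r = 0.5 and 0.7. With a true difference of 0.8, power was 0.79 against 0.88 at r = 0.5, and 0.78 against 0.97 at r = 0.7.

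**5. If the ANOVA were run on change from baseline.** The SD becomes 1.5 × √(2(1 − r)), and power is 0.65, 0.79 and 0.95 at r = 0.3, 0.5 and 0.7. Each is below ANCOVA.

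**6. Compared with recruiting more patients.** The allocation list has 120 slots, 59 iron and 61 placebo by count, so ten more than 2 × 55 = 110. Filling all 120 gives unadjusted power 0.83 and half-width 0.542. ANCOVA at r = 0.3 with 110 patients gives 0.83 and 0.541, so a modest correlation is worth about the ten spare slots.

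**7. Transferrin saturation.** Entry below 20% narrows the spread of the baseline value, which lowers its correlation with the outcome. If it halves the baseline SD (assumption, u = 0.5), r' = r·u / √(1 − r² + r²u²), so 0.3, 0.5 and 0.7 become 0.16, 0.28 and 0.44. The low end of the table is the fair expectation for this outcome.

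**8. Missing readings.** With an assumed 40 per arm having a value, ANOVA has power 0.65 and ANCOVA at r = 0.3 has 0.69. Adjustment does not make up for missing readings.

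**The case against.** The strongest objection is scope. The analysis plan is not shown, covariate adjustment of secondary outcomes is often settled there, and the test named is valid. The ANOVA sentence is also generic and does not exclude other models. It is true that the plan may add adjustment. But the Protocol does not leave the method open: it names one, it is the less efficient choice, and nothing else in the document modifies it.

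The second objection is that the gain is unknown. The 18-point figure needs r = 0.7, which nothing in the Protocol supports; at r = 0.3 the interval is only 4.6% narrower. This stands, and is why the result is given as a range. It does not favour ANOVA, since an uninformative covariate costs nothing measurable.

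Third, availability is not equally certain. The iron-deficiency criterion in Section 4.1 is garbled and does not say clearly whether both measurements are required, so a transferrin saturation for every patient needs confirming. A pre-randomisation haemoglobin is inferred from the daily blood count. A baseline ferritin is not stated. These points limit where the change applies.

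Fourth, dialysis lowers creatinine directly, so a creatinine comparison mixes renal recovery with renal support under either method. That is a real limit on interpretation, and ANCOVA does not remove it.

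**Conclusion.** The point holds. For its continuous secondary outcomes the Protocol names a valid but inefficient test when better use of values already taken is possible. On the Protocol's inputs, with every patient having a reading, adjustment raises power from 0.79 to between 0.80 and 0.97 and narrows the interval by 0.5% to 29% as the assumed correlation goes from 0.1 to 0.7. The power figures assume that the unnamed variable in the sample size is one of these outcomes, apparently haemoglobin.

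It is a worthwhile improvement rather than a threat to the trial: secondary outcomes only, no bias, MAKE30 untouched. Confidence in the size of the gain is moderate, because the Protocol gives no correlation and the haemoglobin baseline is inferred.

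**What to change.** Replace the ANOVA sentence as follows.

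- For haemoglobin, creatinine and transferrin saturation, at discharge and at 28 days after discharge, use ANCOVA of the outcome on arm plus the same variable's last value before randomisation. Report the adjusted difference with its 95% CI.
- For creatinine, use the pre-randomisation value as covariate, not the reference baseline creatinine that appears in the entry criteria and the MAKE30 definition.
- Analyse creatinine on the log scale and report a ratio of geometric means with its 95% CI. This also gives a method for skewed data, which the Protocol foresees but does not provide for.
- Treat ferritin the same way, on the log scale, only if a baseline value is collected.
- Report the number of patients per arm with a value at each reading, since ANCOVA does not resolve values missing through death or loss.

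The cost is analysis wording: no new visit, sample or patient. Two checks are needed first: that a pre-randomisation haemoglobin is recorded for each patient, and that a transferrin saturation is too. Section 1.2 gives a trial period of August 2022 to December 2023 and this version is dated June 2023, so the change should be a dated amendment made before anyone sees outcome data by arm.

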### 4.1 INCLUSION AND EXCLUSION CRITERIA

#### criteria of **inclusion**:

Hospitalized patients with ARD, will be defined as the diagnosis using the KDIGO criteria of serum creatinine (Cr); Patients with AKI  $> 18$  and  $< 85$  years, baseline creatinine  $< 2$  mg/dL and with written informed consent will be included.

Iron deficiency according to the criteria of the 2: serum iron  $< 13$  ng/dL, transferrin saturation  $< 20\%$ .

Version 2.0, 29 June 2023

Effect of intravenous iron repletion on renal function in patients with iron deficiency and acute kidney injury, clinical trial. June 2023, HCG/CEI-1232/22

[name] [contact], [name] GUADALAJARA, JAL

# Old Civil Hospital of Guadalajara "FRAY ANTONIO MAYOR"

Teaching Subdirectorates  
Research Coordination

## 4.2 VARIABLES UNDER STUDY

Exposure variable is the administration of iron dextran in an infusion bolus as a loading strategy.  
Dependent variables will be the value of renal function by eGFR, hemoglobin, iron deficiency, renal function and safety parameters.

## 4.4 ETHICAL ASPECTS

YO.	RESEARCH WITHOUT RISK	RESEARCH WITH	
II.	MINIMAL RISK	RESEARCH WITH RISK	XXXX
III.	GREATER THAN MINIMAL		

# Old Civil Hospital of Guadalajara "FRAY ANTONIO MAYOR"

Teaching Subdirectorato  
Research Coordination

Letter of consent attached to the protocol

Visual summary of the study

Version 2.0, 29 June 2023

Effect of intravenous iron repletion on renal function in patients with iron deficiency and acute kidney injury, clinical trial. June 2023, HCG/CEI-1232/22

[name] [contact], [name] GUADALAJARA, JAL

# *Old Civil Hospital of Guadalajara* "FRAY ANTONIO MAYOR"

Teaching Subdirectorates  
Research Coordination

5.1 SCHEDULE OF ACTIVITIES ATTACH  
FORMAT

Version 2.0, 29 June 2023

Effect of intravenous iron repletion on renal function in patients with iron deficiency and acute kidney injury, clinical trial. June 2023, HCG/CEI-1232/22

[name] [contact], [name] GUADALAJARA, JAL

## Old Civil Hospital of Guadalajara "FRAY ANTONIO MAYOR"

Teaching Subdirectorato  
Research Coordination

